1.4.4 Inter-observer agreement

Variation in the interpretation of US and TAB will be evaluated by comparing raters' interpretations of US and TAB against expert review and agreement between raters' interpretations. The following will be reported:

Raters versus US expert review	Agreement between raters' assessment of US and expert review
Raters versus TAB expert review	Agreement between raters' assessment of TAB and expert review
US raters' agreement	Multi-rater kappa with 95% confidence interval
TAB raters' agreement	Multi-rater kappa with 95% confidence interval

1.4.5 Reference diagnosis evolution and influences

Additional analyses will investigate how the diagnosis changes across the patient's follow-up. The number and percentage of patients whose clinical diagnosis changes between two weeks and six months will be presented, and the characteristics of these patients will be described qualitatively.

The role of various diagnostic tests in reaching the diagnosis of GCA will be reported. Finally, the utility of BVAS and VDI as potential assessment tools for GCA will be investigated using ROC analysis. The BVAS score (range 0-63) is calculated as described in Mukhtyar et al (2009), details of which are provided in Appendix 1; the VDI score (range 0-64) is calculated as described in Exley et al (1997), details of which are provided in Appendix 2.

The following summaries will be presented:

Diagnosis evolution	The number and percentage of patients with a diagnosis of GCA and each alternative diagnosis at two weeks and six months, and the number and percentage of patients whose diagnosis changed between two weeks and six months.
Influences on GCA diagnosis	The proportion of GCA diagnoses which were recorded as being influenced by each of the following: symptoms, signs, blood abnormalities, TAB or other characteristics, at both 2 weeks and 6 months.
Associates with reference diagnosis	The reference diagnosis in relation to various attributes including BVAS and VDI

1.4.6 Modelling of alternative methods to diagnose GCA

The findings from 3.4.1-3.4.5 above will be brought together to input into a decision model for diagnosing GCA. The aim will be to assess whether alternative diagnostic strategies could be employed in relation to subgroups or characteristics. Specifically:

- Whether US followed by TAB is necessary in all patients (US alone may conceivably be used as a rule in/rule out for TAB)
- Which (if any) subgroups of the cohort could be diagnosed without the need for TAB and/or US

Testing strategies will be based on pre-test assessment of patients being at high, medium, or low risk of having GCA.

The accuracy of the dual US-TAB approach and alternative approaches will be reported. Models will be validated internally using cross-centre model fitting, temporal model fitting and bootstrap methods. Logistic regression will be employed, and goodness-of-fit will be tested via Hosmer-Lemeshow test (Hosmer & Lemeshow 2000).

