3.4.2 Performance of US and TAB in relation to patient & disease characteristics

Several additional analyses are planned around the accuracy of US and TAB in relation to different characteristics of the disease and subgroups of patient.

Analyses will be carried out using logistic regression in which the outcome is the reference diagnosis. The performance of US across each characteristic will be assessed, initially one characteristic at a time, by fitting the US diagnosis, the characteristic and their interaction term. A receiver-operator characteristic (ROC) curve will be produced to assess the sensitivity and specificity across different levels of the covariate. The same procedure will be used to assess the performance of TAB.

Following on from this, further modelling will be undertaken to evaluate different strategies for the detection of GCA. The performance of the following strategies will be assessed:

1. *Standard diagnosis (“how does the standard method perform?”)*

1a. TAB alone

1b. TAB plus additional potential prognostic factors collected at baseline (e.g. age, history, BVAS)

2. *Experimental diagnosis (“how do the standard and test methods perform together?”)*

2a. TAB plus US (independently) alone

2b. TAB plus US (either/or positive) alone

2c. TAB plus US (interaction) alone

2d. TAB plus US (independently), plus additional baseline factors

- 2e. TAB plus US (either/or positive), plus additional baseline factors
- 2f. TAB plus US (interaction) , plus additional baseline factors

3. *Reduced-experimental diagnosis (“is a TAB always necessary?”)*

- 3a. US alone
- 3b. US plus additional baseline factors
- 3c. US (+ vs -) plus TAB (+ vs – in US -) alone
- 3d. US (+ vs -) plus TAB (+ vs – in US -), plus additional baseline factors

Models will be built using logistic regression, with diagnostic ability assessed by sensitivity, specificity and the c-statistic.

Depending on the level of agreement and the number of positive cases, some of the analyses may not be possible due to collinearity. Special care will be taken to avoid overfitting and sparse cells.

Models will be internally validated using bootstrap methods to assess reproducibility.

Accuracy of US in relation to scan findings

The prevalence of the following specific findings will be tabulated:

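### The Hosmer-Lemeshow test is the SAP's only goodness-of-fit check; it says nothing about saturated models and little about over-extreme risks, and no calibration measure is named for the planned validation.

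*SAP*

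**What the plan says.** SAP 3.4.2 lists logistic strategies for detecting GCA. Six use test results only: 1a (TAB), 3a (US), "2a. TAB plus US (independently) alone", "2b. TAB plus US (either/or positive) alone", "2c. TAB plus US (interaction) alone" and "3c. US (+ vs -) plus TAB (+ vs – in US -) alone". The other six (1b, 2d, 2e, 2f, 3b, 3d) add baseline factors, given only by example, as in "1b. TAB plus additional potential prognostic factors collected at baseline (e.g. age, history, BVAS". Diagnostic ability is to be judged by sensitivity, specificity and the c-statistic, with bootstrap internal validation. On model size the section says "Special care will be taken to avoid overfitting and sparse cells".

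SAP 1.4.6 takes the findings of the preceding sections into a decision model. It asks whether TAB is needed in all patients and which subgroups could do without TAB or US. It plans cross-centre, temporal and bootstrap validation, and adds that "goodness-of-fit will be tested via Hosmer-Lemeshow test". No grouping, degrees of freedom or rule for ties is given. It also says: "Testing strategies will be based on pre-test assessment of patients being at high, medium, or low risk".

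**The concern.** A model whose risks may help to identify patients who could be diagnosed without TAB should give risks that agree with what is observed in new patients. Of the measures the SAP names, only the Hosmer-Lemeshow test compares predicted with observed risk. The c-statistic depends on ranking alone, so it does not change when all linear predictors are stretched. Sensitivity and specificity depend only on which side of a cut-off a patient falls.

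The Hosmer-Lemeshow test suits this job poorly in two ways. Most of the test-only models are saturated and leave nothing to test. The models with baseline factors would be tested on the data that fitted them, where risks that are too extreme hardly show. A non-significant result could then be read as reassurance that it does not provide.

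**Working it through.** The SAP attaches no figure to this test, so there is none to reproduce.

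**Inputs from the SAP (2.1):** N = 402; prevalence 80%; sensitivity 76% for TAB and 87% for US; expected US specificity 96%. Expected non-GCA patients: 0.20 × 402 = 80.4, about 80. This smaller group limits model size.

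**Assumed, because the SAP does not give them:** TAB specificity 96%; 5 to 30 baseline factors, of which three are informative (shift 0.3 SD each) and the rest noise; all factors kept in the model.

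**Step 1: test-only strategies.** The statistic is the sum over groups of (O − E)² / [E(1 − E/n)], where O and E are the observed and expected GCA cases among the n patients of a group. It is referred to chi-squared on g − 2 degrees of freedom. Patients with the same test results share one predicted risk. With ties kept together, g is therefore at most the number of covariate patterns. When parameters equal patterns, the likelihood equations force O = E in every group.

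| Strategy | Patterns | Parameters | Statistic | g − 2 |
|---|---|---|---|---|
| 1a, 2b, 3a | 2 | 2 | 0 | 0 (undefined) |
| 3c | 3 | 3 | 0 | 1 (p = 1 always) |
| 2c | 4 | 4 | 0 | 2 (p = 1 always) |
| 2a | 4 | 3 | not fixed at 0 | 2 |

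A numerical check gave statistics of about 1e-23 for the saturated models. For 2a the true residual degrees of freedom are 4 − 3 = 1. Using g − 2 = 2 gave a simulated size of about 2.7%, against 5.6% with 1 degree of freedom. Five of the six strategies are therefore untestable. This step needs no assumption about effects.

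**Step 2: models with baseline factors.** Models 1b, 3b and 2d were fitted to simulated trials of 402, with 400 replicates per setting. The Hosmer-Lemeshow test was run on the fitting data at 5%. The calibration slope b, from logit P(GCA) = a + b × linear predictor, was taken in 5,000 new patients. A slope below 1 means risks that are too extreme. Ranges are across the three models.

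| Factors | Non-GCA patients per factor | Test rejects | Median slope | Slope below 0.9 |
|---|---|---|---|---|
| 5 | 80/5 = 16 | 4-8% | 0.89-0.93 | 41-52% |
| 10 | 80/10 = 8 | 5-10% | 0.82-0.88 | 62-72% |
| 20 | 80/20 = 4 | 9-11% | 0.65-0.75 | 91-96% |
| 30 | 80/30 = 2.7 | 11-15% | 0.45-0.64 | 100% |

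**Step 3: sensitivity to the assumptions.**
- With lower assumed accuracies (TAB 60%/95%, US 70%/85%) and 5 to 20 factors, rejection was 4-11% and median slopes ran from 0.92 down to 0.70.
- With US plus 5 to 20 factors and a 0.4 SD shift for the three informative ones, rejection was 8-12% and the slope fell from 0.89 to 0.75.
- A further run gave rejection of 7%, 9% and 11% with 5, 10 and 20 factors, and median slopes of 0.92, 0.86 and 0.74.

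All settings show the same pattern: rejection stays slightly above the nominal 5% while the slope falls well below 1.

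**The case against.** The strongest reply is that the SAP gives overfitting to other tools. Cross-centre, temporal and bootstrap validation stand beside the Hosmer-Lemeshow sentence, and 3.4.2 promises care about overfitting. This stands. A reader might infer that the SAP relies on the Hosmer-Lemeshow test to catch overfitting, but the text does not say so. What remains is that no calibration measure is named for that validation, and validating the c-statistic cannot show that risks are too extreme.

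Second, the test appears in 1.4.6 and the strategies in 3.4.2, where it is not mentioned. That it would be run on every test-only strategy is an inference. A saturated model's predicted risks are simply the observed proportions, so no lack of fit is missed. This also stands and limits Step 1 to an empty p-value.

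Third, a reader might infer that the logistic models' predicted risks decide who goes without TAB. The SAP speaks of a pre-test assessment and does not give its source. Every listed model includes US or TAB or both, and 3.3 records the clinician's initial certainty of GCA, which is another possible source. The documents support only the conditional statement that model risks may inform these choices.

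Fourth, the size rests on assumed factors with no selection or shrinkage, and 20 or more factors is the heavy end. That is fair. Nor can a slope be turned into one definite error in risk. At a slope of 0.80, a predicted 5% (logit −2.94) becomes about 9% with a zero intercept (0.80 × −2.94 = −2.36), or about 11% if shrunk towards the prevalence (1.39 + 0.80 × (−2.94 − 1.39) = −2.08). The SAP fixes neither anchor. Predicted risks below 5% were also rare in simulation: a median of 0.1%, 0.5% and 1.9% of patients with 5, 10 and 20 factors.

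**Conclusion.** The point holds in a limited form and is minor. It is certain that the Hosmer-Lemeshow test carries no information for strategies 1a, 2b, 2c, 3a and 3c, although the harm is confined to a meaningless p-value if it is run there. For the models with baseline factors, a non-significant in-sample result is weak evidence of good calibration. With 5 to 20 factors it would be expected in roughly 88-96% of fits, while the median slope in new patients ranges from about 0.9 down to 0.65-0.75. Those figures depend on the assumed number and strength of factors and on all being retained. The gap in the plan is that sensitivity, specificity, the c-statistic and this test together give no informative check on whether predicted risks are too extreme. The models are secondary to the accuracy comparison in 3.4.1, which is unaffected.

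**What to change.** In SAP 1.4.6, replace the goodness-of-fit clause with text to this effect: the Hosmer-Lemeshow test will not be used for saturated models, and a non-significant result will not be taken as evidence of adequate fit for any other model. For each model with baseline factors, the optimism-corrected calibration slope and intercept and a calibration plot will be reported from the planned bootstrap.

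Shrinking the coefficients by the corrected slope is optional, and worth considering if predicted risks or risk groups from these models are reported. It would also help to state whether the high, medium and low pre-test risk comes from clinicians or from a model.

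The cost is a sentence or two in the SAP, a little more output from resampling already planned, and the loss of a single goodness-of-fit p-value. No new data are needed.

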1.4.7 The following summaries will be reported **Cost-effectiveness**

The cost-effectiveness of different models will be quantified in a separate analysis plan

1.4.8 Health-related quality of life

Health-related quality of life for the cost-effectiveness analysis will be measured at each assessment using the EuroQol EQ-5D at baseline, 2 week and 6 month visits. The EQ-5D health state will be derived from the questionnaire using UK population norms. The EQ-5D thermometer scale health state, as measured in response to the question “What is your own health state today”, will be scored between 0-100.

EQ-5D health state	The EQ-5D health state at each time point and the change from baseline at 2 weeks & six months
EQ-5D thermometer health state	The EQ-5D thermometer health state at each time point and the change from baseline at 2 weeks & six months

1.4.9 Steroid usage and side effects

Steroid usage will be recorded at baseline, 2 weeks and 6 months.

Steroid usage	The number and percentage of patients on steroids at presentation and at two week visit; the average daily dose, the average length of time spent on steroids, and the estimated cumulative exposure.
Side effects	The number and percentage of patients experiencing each side effect

3.5 Safety outcomes

The following summaries will be presented:

Conditions and symptoms by time point	The number and percentage of participants with each condition or symptom by time point
AEs	The number and percentage of participants reporting each AE following study start, by relatedness to US, TAB and overall
Serious AEs (SAEs)	The number and percentage of participants reporting an SAE following study start

Steroid side effects are described previously and will not be repeated herein.

4 Modifications to the original protocol analysis statement

Not applicable.

5 References

ICH Harmonised Tripartite Guideline Topic E6(R1): Guideline for Good Clinical Practice (1996). Available at: http://www.ich.org/fileadmin/Public_Web_Site/ICH_Products/Guidelines/Efficacy/E6_R1/Step4/E6_R1__Guideline.pdf (last accessed 19June 2012)

Pepe MS. *The statistical evaluation of medical tests for classification and prediction*. Oxford, OUP: 2003.

6 Appendix

Appendix 1: Birmingham Vasculitis Activity Score (Adapted by permission from BMJ Publishing Group Limited. Modification and validation of the Birmingham Vasculitis Activity Score (version 3), Mukhtyar C, Lee R, Brown D, Carruthers D, Dasgupta B, Dubey S, *et al.*, 68, 2009.)

1. If all manifestations are persistent (i.e. the “persistent” box is ticked), the scores from column 2 are used. Otherwise, the scores from column 3 are used. (Items for which column 2 is marked “n/a” cannot be considered persistent)
2. The scores are applied to each ticked manifestation. If no manifestations are recorded, a score of zero is applied.
3. Within each domain, a maximum score is applied. For example, the sum of scores for “general” manifestations cannot be greater than 3 (2 if all persistent).

Manifestation	Persistent	New / Worse
1. General (Maximum score)	2	3
Myalgia	1	1
Arthralgia or arthritis	1	1
Fever $\geq 38^{\circ}$ C	2	2
Weight Loss ≥ 2 kg	2	2

2. Cutaneous (Maximum score)	3	6
Infarct	1	2
Purpura	1	2
Ulcer	1	4
Gangrene	2	6
Other skin vasculitis	1	2

3. Mucous Membranes / eyes (Maximum score)	3	6
Mouth ulcers / granulomata	1	2
Genital ulcers	1	1
Adnexal inflammation	2	4
Significant proptosis	2	4
Scleritis / Episcleritis	1	2
Conjunctivitis / Blepharitis / Keratitis	1	1
Blurred vision	2	3
Sudden visual loss	n/a	6
Uveitis	2	6
Retinal changes (vasculitis, thrombosis / exudate / haemorrhage)	2	6

4. Ear, Nose & Throat (Maximum score)	3	6
Bloody nasal discharge / crusts / ulcers / granulomata	2	4
Paranasal sinus involvement	1	2

Subglottic stenosis	3	6
Conductive hearing loss	1	3
Sensorineural hearing loss	2	6

5. Chest (Maximum score)	3	6
Wheeze	1	2
Nodules or cavities	n/a	3
Pleural effusion / pleurisy	2	4
Infiltrate	2	4
Endobronchial involvement	2	4
Massive haemoptysis / alveolar haemorrhage	4	6
Respiratory failure	4	6

6. Cardiovascular (Maximum score)	3	6
Loss of pulses	1	4
Valvular heart disease	2	4
Pericarditis	1	3
Ischaemic cardiac pain	2	4
Cardiomyopathy	3	6
Congestive cardiac failure	3	6

7. Abdominal (Maximum score)	4	9
Peritonitis	3	9
Bloody diarrhoea	3	9
Ischaemic abdominal pain	2	6

8. Renal (Maximum score)	6	12
Hypertension	1	4
Proteinuria	2	4
Haematuria	3	6
Serum creatinine 125-249 $\mu\text{mol/L}$	2	4
Serum creatinine 250-499 $\mu\text{mol/L}$	3	6
Serum creatinine $\geq 500 \mu\text{mol/L}$	4	8
>30% rise in creatinine or >25% fall in creatinine clearance	n/a	6

9. Nervous system (Maximum score)	6	9
Headache	1	1
Meningitis	1	3
Organic confusion	1	3
Seizures (not hypertensive)	3	9

Stroke	3	9
Spinal cord lesion	3	9
Cranial nerve palsy	3	6
Sensory peripheral Neuropathy	3	6
Mononeuritis Multiplex	3	9

Appendix 2: Vasculitis Damage Index (Republished with permission of John Wiley and Sons Inc, from Development and initial validation of the Vasculitis Damage Index for the standardized clinical assessment of damage in the systemic vasculitides, Exley AR, Bacon PA, Luqmani RA, Kitas GD, Gordon C, Savage CO, Adu D, 40(2), 1997; permission conveyed through Copyright Clearance Centre Inc.)

The VDI records the presence or absence of 64 specific conditions since the onset of suspected GCA. The total VDI score is defined as the total number of items scored, ranging from zero to a theoretical maximum of 64.

VASCULITIS DAMAGE INDEX (VDI) This is for recording organ damage that has occurred in patients since the onset of suspected GCA Patients often have co-morbidity before onset of suspected GCA, which must not be scored Record features of active disease using the Birmingham Vasculitis Activity Score (BVAS) A new patient should usually have a VDI score of zero , unless: (a) they have had suspected GCA for more than three months and (b) the damage has developed or become worse since the onset of suspected GCA		
Musculoskeletal?  Yes  No If yes:  Significant muscle atrophy or weakness  Deforming/erosive arthritis  Osteoporosis/vertebral collapse  Avascular necrosis  Osteomyelitis Skin/Mucous membranes?  Yes  No If yes:  Alopecia  Cutaneous ulcers  Mouth ulcers Ocular?  Yes  No If yes:  Cataract  Retinal change  Optic atrophy  Visual impairment/diplopia  Blindness in one eye  Blindness in second eye  Orbital wall destruction ENT?  Yes  No If yes:  Hearing loss  Nasal blockage/chronic discharge/crusting  Nasal bridge collapse/septal perforation  Chronic sinusitis/radiological damage  Subglottic stenosis (no surgery)  Subglottic stenosis (with surgery)	Pulmonary?  Yes  No If yes:  Pulmonary hypertension  Pulmonary fibrosis  Pulmonary infarction  Pleural fibrosis  Chronic asthma  Chronic breathlessness  Impaired lung function Cardiovascular?  Yes  No If yes:  Angina/angioplasty  Myocardial infarction  Subsequent myocardial infarction  Cardiomyopathy  Valvular disease  Pericarditis \geq 3 mths or pericardectomy  Diastolic BP \geq 95 or requiring antihypertensives Peripheral vascular disease?  Yes  No If yes:  Absent pulses in one limb  2 nd episode of absent pulses in one limb  Major vessel stenosis  Claudication >3 mths  Minor tissue loss  Major tissue loss  Subsequent major tissue loss  Complicated venous thrombosis	Gastrointestinal?  Yes  No If yes:  Gut infarction/resection  Mesenteric insufficiency / pancreatitis  Chronic peritonitis  Oesophageal stricture/surgery Renal?  Yes  No If yes:  Estimated/measured GFR < 50%  Proteinuria > 0.5g/24hr  End stage renal disease Neuropsychiatric?  Yes  No If yes:  Cognitive impairment  Major psychosis  Seizures  Cerebrovascular accident  2nd cerebrovascular accident  Cranial nerve lesion  Peripheral neuropathy  Transverse myelitis Other?  Yes  No If yes:  Gonadal failure  Chemical cystitis  Marrow failure  Malignancy  Diabetes  Other Total VDI Score*  Record the number of positive items (1 point for each).

The VDI score can either increase or remain the same over time. Remember to carry forward any previous items of damage
